2.4.9 Cold pain tolerance (aim #2 and #3)

A cold pain tolerance (CPT) test, with the participants comfortably seated while immersing the right foot into a tank 5cm above the ankle joint (13) in cold water at $\sim 2^{\circ}\text{C}$ ($1^{\circ} - 4^{\circ}$) (77) will be used to determine participants pain tolerance before and after both acute exercise and long-term training. Water temperature will be adjusted through immersion of ice until achieving the desired temperature. Participants will be instructed to remove their foot from the water at any time when unable to support strong cold nociception sensation. In aim #2 it will be assessed 0-15 min post-exercise or rest (after pressure pain threshold assessment). Once breathing frequency might modify the subjective level of cold pressor pain (77), we will fix ventilatory frequency using a metronome for standardize the duration of the inspiration and expiration phases (2s each).

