2.3.2 Study design

Each intervention group will perform 6 weeks of exercise training (resistance, supramaximal and endurance training). Participants allocated to each training group will be evaluated before and after training. On one day participants will be tested for pressure pain threshold and cold pain tolerance with concomitant measures of AP and HRV. The influence of metaboreflex activation (maintained submaximal isometric contraction followed by blood flow occlusion) on H-reflex and V-wave parameters will also be measured. On another day, participants will be evaluated for resting AP and HRV, neuromuscular adaptations and performance. The experimental design is illustrated in figure 3.

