2.4.13 Statistical analysis (aim #1, #2 and #3)

Normality will be verified through the Shapiro-Wilk test. Univariate ANOVAs will be used to explore differences in the impact of blood-flow occlusion vs. non-blood flow occlusion on each H-reflex and V-wave variable (aim #1). Repeated measures ANOVA will be computed to determine significant main effects for time (pre- vs. post-acute exercise), condition (resistance vs. supramaximal vs. endurance exercise) and time-by-condition interactions on pain tolerance/threshold/ratings, AP, HRV and H-

reflex parameters and V-wave amplitude with metaboreflex activation (aim #2). Repeated measures ANOVA will be computed to determine significant main effects for time (pre- vs. post training), condition (resistance vs. supramaximal vs. endurance training) and time-by-condition interactions on exercise performance, pain tolerance/threshold/ratings, AP, HRV, H-reflex parameters and V-wave amplitude with metaboreflex activation, and neuromuscular adaptations to training (aim #3). Correlations between the impact of exercise or training on pain tolerance/threshold/ratings and performance on H-reflex, V-wave, AP and HRV variables will also be explored. Significance level will be set at $p < 0.05$. All data will be treated using SPSS 25.0 for statistical analysis.

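### The cold-tolerance bath has a target of about 2 °C but an accepted band of 1 to 4 °C, with no rule to record the temperature or match it within a man, so a compliant pre-post pair can differ by up to 3 °C

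*Combined protocol and SAP*

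**What the plan says.** In section 2.4.9 the right foot is immersed "in cold water at $\sim 2^{\circ}\text{C}$ ($1^{\circ} - 4^{\circ}$) (77" (the closing number is a literature reference). Temperature control is one sentence: "Water temperature will be adjusted through immersion of ice until achieving the desired temperature". The endpoint is voluntary withdrawal: "Participants will be instructed to remove their foot from the water at any time when unable to support strong cold nociception sensation". The test is to determine "participants pain tolerance before and after both acute exercise and long-term training".

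The same section standardises breathing explicitly: "we will fix ventilatory frequency using a metronome for standardize the duration of the inspiration and expiration phases (2s each" seconds-in, seconds-out rule is given because breathing may alter cold pain. No comparable within-man rule is given for the water.

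Other measurements come from the same immersion: a visual analogue pain rating every 30 s (2.4.9.1), arterial pressure every minute and continuous heart rate variability (2.4.10).

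In aim #2 each man is tested before and after on two days, exercise and passive rest (2.2.2), so he has four immersions. In aim #3 the two tests are separated by training: "Each intervention group will perform 6 weeks of exercise training" (2.3.2).

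Section 2.4.13 analyses these outcomes by repeated measures ANOVA. For aim #2 it looks for "significant main effects for time (pre- vs. post-acute exercise), condition (resistance vs. supramaximal vs. endurance exercise") and their interaction; for aim #3, for "significant main effects for time (pre- vs. post training), condition (resistance vs. supramaximal vs. endurance training") and their interaction. Neither model has a temperature term.

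**The concern.** How long a man keeps his foot in the water depends on his pain sensitivity and on how cold the water is. A within-man change isolates the first only if the second is held constant. The plan holds it to a 3-degree band common to everyone, not to the man's own earlier value.

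Two things are at stake. Random mismatch inflates the variance of the change score in small groups: 8 per modality in aim #2 (2.2.1) and a goal of at least 8 per group in aim #3 (2.3.1). A systematic difference between pre and post baths would shift the time effect itself. If a warmer bath hurts less, a warmer post-test bath would lengthen tolerance and blunt the pressure and autonomic response together, which is the pattern that section 1.3 predicts from exercise. Because no reading is required, this could not be checked afterwards.

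**Working it through.** **Inputs from the documents.** Target about 2 °C and band 1–4 °C (2.4.9); paired pre-post use (2.4.9); 8 men per modality (2.2.1); significance level 0.05, sidedness not stated (2.4.13). The plan derives no figure from the band, so there is none to reproduce.

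**Assumptions, because the documents are silent.** Temperatures are either uniform over 1–4 °C or triangular over 1–4 °C with mode 2 °C. Pre and post temperatures are independent. Tolerance changes by k = 0.05 to 0.15 log units per °C. The SD of the log change without temperature noise is s = 0.25 to 0.35.

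**Step 1, largest compliant difference.** 4 − 1 = 3 °C.

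**Step 2, typical difference d between two tests.**
- Uniform: variance of one test = 3²/12 = 0.75, so Var(d) = 1.5 and SD(d) = 1.22 °C. Mean absolute difference = 3/3 = 1.0 °C; 11% of pairs differ by more than 2 °C.
- Centred on 2 °C: variance of one test = (1 + 16 + 4 − 4 − 2 − 8)/18 = 7/18 = 0.389, so Var(d) = 0.778 and SD(d) = 0.88 °C. By simulation the mean absolute difference is 0.71 °C, and 1.9% of pairs differ by more than 2 °C.

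**Step 3, rise in the variance of the change.** Relative rise = k² × Var(d) / s².
- Uniform, low end: 0.0025 × 1.5 / 0.1225 = 3%. High end: 0.0225 × 1.5 / 0.0625 = 54%.
- Centred, low end: 0.0025 × 0.778 / 0.1225 = 1.6%, about 2%. High end: 0.0225 × 0.778 / 0.0625 = 28%.

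**Step 4, the same question as power.** Take a comparison of two modalities, 8 v 8, two-sided 0.05, with 80% power when there is no temperature noise. Let 1 °C shift tolerance by r SDs of the change score. Then f = √(1 + r² Var(d)) and power = Φ(2.802/f − 1.960), where 2.802 = 1.960 + 0.842.

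| r (assumed) | Uniform 1–4 °C | Centred on 2 °C | Each test within ±0.5 °C of one value |
|---|---|---|---|
| 0.10 | 79% | 80% | 80% |
| 0.25 | 76% | 78% | 80% |
| 0.50 | 67% | 73% | 78% |

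**Step 5, with matching.** Suppose each later test lies within 0.5 °C of the man's first test, uniformly.
- First test v a later one: Var(d) = 1²/12 = 0.083, largest difference 0.5 °C. The rise is 0.0025 × 0.083 / 0.1225 = 0.2% to 0.0225 × 0.083 / 0.0625 = 3%.
- Two later tests v each other (the second day of aim #2): Var(d) = 0.167, largest difference 1 °C, and the rise doubles to about 0.3–6%. This is the last column of the table.

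**Step 6, where a systematic difference would land.** A drift common to all groups cancels from the time-by-condition interaction but not from the time main effect. Aim #3 describes no untrained group (2.3.2). The aim #2 design has a rest day (2.2.2), but the levels of condition listed in 2.4.13 are the three exercise modalities and do not include rest. As written, neither time effect is protected.

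**The case against.** The plan does name one target for every test and adds ice to reach it, so this is active control around about 2 °C. The target and band carry a citation. Three degrees needs one test at each edge of the band. In aim #2 the pre and post tests fall on the same day, so their temperatures may well be correlated, and independence then overstates the mismatch. The sensitivities are assumed, and a range from 2% to 54% cannot show that the problem is material. Pressure pain threshold (2.4.8) is untouched, the time main effect in aim #2 pools 24 men, and the main hypotheses compare modalities, where a common drift cancels. The 0.5 °C margin is not derived from anything in the documents.

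Most of this stands, and it limits the size of the point. It does not close the gap: no section requires matching, recording or adjustment, and cold tolerance is the only tolerance measure in the plan.

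Three stronger readings are tempting and unsupported. A reader might infer that the changes do contain 3 °C differences; the text only permits them. A reader might infer that a recorded temperature is being left out of the analysis; the plan requires no such record. And a reader might infer that ice handling differs before and after exercise and so produces apparent hypoalgesia; nothing in the documents says so.

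**Conclusion.** The point holds as a cheap improvement, not as a flaw that invalidates the cold-tolerance results. What is certain from the text is that compliant pre-post pairs can differ by up to 3 °C and that no reading is required that would reveal it. Random mismatch costs precision in tolerance, pain ratings, arterial pressure and heart rate variability; bias in the time effect arises only if the bath differs systematically between pre and post.

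The size cannot be established from the documents. The variance ranges (about 2–28% centred, 3–54% uniform) and the power figures depend on the assumed sensitivity, SD, temperature distribution and independence. The centred range fits the stated target better. At the low end the effect is negligible.

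**What to change.** In section 2.4.9, keep the stated target and add three requirements: stir the water; record its temperature at each immersion; and hold each man's later tests, including those on the rest day, within a narrow pre-set margin of his own first test. A margin of 0.5 °C would serve as an example; it is an operational choice.

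In section 2.4.13, state that the recorded temperatures will be reported by group and time point, and that the tolerance analysis will be repeated as a sensitivity check using them, for instance with the pre-post temperature difference as a covariate.

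The cost is a thermometer reading, stirring and some extra ice handling, with no new visit or staff. The downside is a slightly longer set-up between tests. In aim #2 this must still fit the 0–15 min post-exercise window, after pressure pain testing, so the bath should be brought to temperature before exercise ends.

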2.4.9.1 Cold pain ratings (aim #2 and #3)

The participants will be asked to mark the intensity of cold pain sensation using a visual analogue scale (VAS) with a horizontal line of 100mm (78), every 30 s.

2.4.10 Arterial pressure and heart rate variability (aim #1, #2 and #3)

AP will be assessed using an automatic monitor (Tango SunTech Medical Morrisville, NC) during thigh blood flow occlusion procedures to confirm the sustained activation of the metaboreflex. In addition, AP will be measured before and after acute exercise and long-term training during cold pain tolerance testing (every minute). Cardiac autonomic regulation, both before and after acute exercise and long-term training during cold pain tolerance testing, will be assessed continuously from a Polar

R-R recorder (Polar RS 800 CX, Finland) through spectral decomposition of beat-by-beat HRV (79). Resting AP and HRV (continuous recording during 5 min) will also be assessed before and after training.

2.4.11 Negative risk involved in the experiments and control countermeasures (aim #1, #2 and #3)

The risk of injury during the course of the study are minimal. Nevertheless, participants will be asked to report any adverse reaction. Additionally, besides nociception, no past reports indicate complications derived from temporary total blood-flow occlusion (75) nor cold-water limb immersion (77). The application of electrical current to the tibial nerve ~~can~~ generate some discomfort as well as the Wingate testing and the training protocols. Participants will be monitored and supervised during each experimental session. No insurance is foreseen for this study.

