The most commonly proposed mechanism of EIH relies on enhanced descending inhibition by activation of the opioid and cannabinoid systems (5, 18, 20). The contraction of skeletal muscle increases the discharge of mechanosensitive afferents (i.e., A-delta and C fibers) which, in turn, activate central descending opioid analgesic pathways (21, 22). Exercise also increases the release of endogenous cannabinoids (23). The endocannabinoid system is a neuromodulatory system composed of cannabinoid receptors (CB1, CB2), their endogenous ligands, that is, the endocannabinoids (Narachidonyl ethanolamine [AEA] and 2-arachidonoylglycerol [2-AG]), and proteins responsible for their metabolism (24). The presence of cannabinoid receptors in nociceptive-processing areas of the brain and spinal cord suggests that endocannabinoids contribute to the control of pain through the activation of CB1 receptors (24). The circulating levels of endocannabinoids increase after isometric exercise (23). These opioid and cannabinoids pathways have receptors not only throughout the central nervous systems but also at the periphery and can produce analgesia when stimulated (18). Furthermore, there is evidence of an interplay between the endocannabinoid and opioid systems, such that the activation of one system is mediated by the other system (25).

Exercise-induced changes in the cardiovascular system have also been proposed as a mechanism of EIH (18). Exercise causes an increase in blood pressure which results in the activation of baroreceptors, innervated by vagal afferents, that are synaptically connected to pain modulatory brain areas, associated with blood pressure control, that decrease pain sensibility when activated (26, 27). This network is thought to be composed of interconnected areas including the insular and prefrontal cortices, the amygdala, the hypothalamus, the periaqueductal gray, the nucleus tractus solitarius. However, there's still little evidence to support this (28, 29), once acute increases in blood pressure by exercise could not account for the persistence of EIH after exercise (i.e. 15 min after exercise

cessation blood pressure would have presumably returned to baseline values, or indeed be lower) (18).

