isometric contraction followed by blood-flow occlusion) Vs. a control condition (no isometric contraction nor blood flow occlusion), on H-reflex recruitment curve and V wave excitability (aim #1). Since the activation of group III/IV afferents can inhibit the corticospinal pathway (61) we hypothesize that the normalized maximal amplitude and the slope of the ascending limb of the H-recruitment curve will decrease with metaboreflex activation. Additionally, we intend to examine the acute impact of different exercise modalities (resistance, supramaximal and endurance) on nociception sensibility (by the application of a cold tolerance test and by determining pressure pain threshold) (aim #2). This will allow us to investigate the role of different acute exercise paradigms on possible metaboreflex desensitization in its relationship with altered neuromuscular responses at post-exercise time point (attenuated inhibition of H-reflex and V-wave amplitude during metaboreflex activation). Also, once past research has shown that muscle metaboreflex activation reduces the sensitivity of the baroreflex (68), we will measure arterial pressure (AP) and heart rate variability (HRV) during cold pain tolerance testing. Despite all exercise modalities could enhance reducing pain sensibility after exercise, we hypothesize that resistance and supramaximal exercise stimuli will enhance nociceptive tolerance via metaboreflex desensitization compared to that seen with endurance exercise (attenuated increase of AP and sympathetic component of HRV during cold pressor test). Finally, we intend to explore the impact of long-term resistance, supramaximal and endurance training on nociceptive sensibility, using the same tests of aim #2 (aim #3). We hypothesize that chronic EIH will be of greater magnitude after supramaximal and resistance exercise training vs. endurance training. In addition, we hypothesize that decreased nociception will be related with attenuated inhibition of H-reflex and V-wave amplitude and attenuated increase of AP and sympathetic component of HRV during metaboreflex activation after training and this will result in increased exercise performance via heightened H-reflex and V-wave excitability.

2. Research Plan and Methods

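### Section 2.4.10 plans no HRV recording during thigh occlusion (Aim #3) and no same-session rest before the cold immersions (Aim #2), so three of the four hypothesised increases cannot be formed

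*Combined protocol and SAP*

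**What the plan says.** Section 1.3 (Purpose) states two hypotheses about a rise. For Aim #2, resistance and supramaximal exercise, compared with endurance exercise, should show an "attenuated increase of AP and sympathetic component of HRV during cold pressor test". For Aim #3, reduced nociception should go with an "attenuated increase of AP and sympathetic component of HRV during metaboreflex activation after training".

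Section 2.4.10 sets out the recordings:

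- **Thigh occlusion:** AP is taken "during thigh blood flow occlusion procedures to confirm the sustained activation of the metaboreflex". R-R recording is not mentioned.
- **Cold test:** AP is taken every minute. For HRV, "Cardiac autonomic regulation, both before and after acute exercise and long-term training during cold pain tolerance testing, will be assessed continuously from a Polar" recorder.
- **Rest:** "Resting AP and HRV (continuous recording during 5 min) will also be assessed before and after training". This covers Aim #3 only, and section 2.3.2 separates it from the day of the cold and occlusion tests: "On another day, participants will be evaluated for resting AP and HRV, neuromuscular adaptations and performance".

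For Aim #2, section 2.2.2 lists AP and HRV only as measures taken alongside the cold test. Sections 2.4.12 and 2.4.13 define no change from rest for either variable.

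**The concern.** An increase needs two values, one at rest and one under provocation. A claim that the increase is attenuated needs both values before and after the intervention. Where one of them is not recorded, only levels can be compared.

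This matters most in Aim #2. The post-exercise immersion takes place 0-15 min after exercise (section 2.4.9), when the resting level may differ from its pre-exercise value. A lower AP during the second immersion could then reflect a lower starting point, yet be read as a smaller pressor response and so as desensitisation. A higher starting point could hide a real attenuation.

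In Aim #3 the gap is simpler. The hypothesis names HRV during metaboreflex activation, and the measurement section does not collect it. R-R intervals that were never recorded cannot be recovered at the analysis stage.

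**Working it through.** The plan gives no figure to reproduce here. The check has two parts.

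**1. Which hypothesised increases can be formed from the written text?**

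| Increase named in section 1.3 | Value under provocation (2.4.10) | Resting value (2.4.10, 2.3.2) | Can it be formed? |
|---|---|---|---|
| Aim #2, AP, cold test | Yes, every minute | None in the session | No |
| Aim #2, HRV, cold test | Yes, continuous | None | No |
| Aim #3, HRV, metaboreflex activation | None stated | Yes, another day | No |
| Aim #3, AP, metaboreflex activation | Yes | Yes, another day | Yes, with a different-day reference |

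Three of the four cannot be formed. Section 2.4.1 does include a baseline blood pressure for every participant. It is not tied to an immersion, cannot reflect the post-exercise state, and supplies no HRV.

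**2. What does a comparison of during-test levels estimate instead?**

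Write level = rest + rise. Then

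level(post) − level(pre) = [rest(post) − rest(pre)] + [rise(post) − rise(pre)].

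The hypothesis concerns the second bracket. The planned Aim #2 data give only the sum. Example with assumed figures for systolic AP:

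- Before exercise: 120 at rest, 150 in the cold test; rise 150 − 120 = 30 mmHg.
- After exercise: 110 at rest, 140 in the cold test; rise 140 − 110 = 30 mmHg.
- Change in rise: 30 − 30 = 0. Change in level: 140 − 150 = −10 mmHg.

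With no true change in the rise, an assumed resting shift of 5, 10 or 15 mmHg gives a false change of 5, 10 or 15 mmHg, with the sign of the shift. The same identity holds for any HRV index.

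For the two Aim #2 ANOVA terms in section 2.4.13, the main effect of time carries the average resting shift. The time-by-condition interaction carries the difference in shift between modalities, so a shift common to all three would cancel there.

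**The case against.** Several parts of the case against stand.

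- **A reader might infer that none of the increases can be calculated.** That goes too far. The Aim #3 AP rise can be formed against rest from another day, and so can Aim #3 cold-test rises, although the latter are not what the Aim #3 hypothesis names.
- **A reader might infer that Aim #2 rests its desensitisation claim on the cold test alone.** It does not. Sections 1.3 and 2.2.2 also test desensitisation through H-reflex and V-wave responses under contraction and occlusion, 15-30 min after exercise (section 2.4.7). The cold-test AP and HRV are an additional marker, so what to call that response is largely a matter of interpretation.
- **A reader might take section 1.1 as saying that AP is below baseline at the immersion.** The sentence, "cessation blood pressure would have presumably returned to baseline values, or indeed be lower", refers to 15 min after exercise, which is the end of the 0-15 min window and not the whole of it. Its first alternative would mean no shift at all.
- **A reader might conclude that the modality comparison is biased, or that residual vagal withdrawal pushes LF/HF in a known direction.** The documents give nothing on whether the resting shift differs by modality, or on its direction for HRV. The defect is that the planned data could not reveal such a difference.
- **The text is partly ambiguous.** Section 2.4.13 lists AP and HRV beside H-reflex and V-wave variables with metaboreflex activation, which could be read as including HRV under occlusion. Section 2.4.10 does not say when the cold-test recording starts. Figures 2 and 3 are not shown and may mark a rest period.

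None of this supplies the missing measurements. If section 2.4.13 does intend HRV under occlusion, it calls for data that section 2.4.10 does not provide. The Aim #2 passive-rest day does not help either: rest does not reproduce a post-exercise shift, and the planned Aim #2 ANOVA has no exercise-versus-rest term.

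**Conclusion.** The point holds for three of the four increases. As written, the HRV part of the Aim #3 metaboreflex hypothesis cannot be tested, and the Aim #2 cold-test rises in AP and HRV cannot be separated from a post-exercise shift in resting level. The Aim #3 AP rise can be formed with a weaker, different-day reference.

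The possible error in Aim #2 equals the resting shift. The 5 to 15 mmHg range is an assumption, in either direction, because the documents give no value. The conclusion concerns the written text and assumes that the figures not shown specify no additional recordings.

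This should be fixed before data collection, but it does not threaten the study as a whole. AP and HRV are one mechanistic strand. Pain threshold and tolerance, H-reflex, V-wave and performance outcomes do not depend on it, and during-test levels can still be compared and reported as levels.

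**What to change.** 1. **Cold test.** In section 2.4.10, add a seated AP reading and a short R-R recording immediately before every immersion, on exercise and rest days, with the same paced breathing as in section 2.4.9 (2 s in, 2 s out). In section 2.4.13, analyse the change from that value.
2. **Occlusion.** Take AP at a seated rest before the contraction, and make the change during occlusion the Aim #3 AP outcome. Record R-R intervals at that rest and during occlusion, with the same paced breathing at both; section 2.4.9 currently specifies pacing for the cold test only. The occluded H-curve block lasts 22 × 4 × 3 s = 264 s = 4.4 min. Its stimuli come every 3 s, and 1/3 s ≈ 0.33 Hz lies inside the plan's HF band of 0.15-0.4 Hz, so HF and LF/HF from that block need cautious interpretation. Alternatively, remove HRV from the Aim #3 metaboreflex hypothesis.
3. **Wording.** Reconcile sections 1.3, 2.4.10 and 2.4.13 on whether HRV is analysed under metaboreflex activation. Relabelling the cold-test response as a cold-pain pressor response is optional.

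The cost is protocol wording, a few minutes of recording per session with devices already in use, and some extra HRV processing. The main drawback is that the recording before the post-exercise immersion uses part of the 0-15 min window. No sample size changes.
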